4.4.4. Laboratory Data

Clinical laboratory values will be expressed in Système International (SI) units.

The actual value and change from baseline (Day 1) to each on-study evaluation will be summarized for each clinical laboratory parameter, including hematology, clinical chemistry, urinalysis, and coagulation and presented by treatment and dose and separately by concentration. In the event of repeat values, the last non-missing value per study day/time will be used. Laboratory results recorded at unscheduled visits will not be tabulated.

Severity of clinical laboratory measurements will be determined using Common Terminology Criteria for Adverse Events (CTCAE) criteria when available.

Shift tables of change in CTCAE grade of laboratory parameters from baseline to worst value and from baseline to last value on study will be presented. Both scheduled and unscheduled visits will be included in shift tables.

All laboratory data will be provided in by-subject data listings, including results of pregnancy tests, alcohol tests, and serology. A subset listing will be presented for all laboratory values with CTCAE grade ≥ 3 .

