**Treatment Period****Day -1**

Subjects will come to the CPU on Day -1 and will be interviewed by study personnel regarding concomitant medications and any change in their health status or diet since screening. Inclusion/exclusion criteria will be reconfirmed and eligible subjects will undergo the following procedures:

- Physical examination.
- Weight.
- Blood and urine safety tests (see Section 7.3.9 for more details).

The subjects will stay confined till the morning of Day 3.

The following assessments will be done :

- UDS.
- Urine pregnancy test (all women regardless of childbearing potential).
- Serum alcohol test.
- Urine sample for creatinine and renal injury biomarker testing (see Section 7.5.1).
- Assessment of AEs and concomitant medications.

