#### Postdose

- After dosing, subjects will remain confined to bed for four hours (except when required to void). They will then be allowed to move freely within the ward but must refrain from strenuous physical activity for the duration of the study.
- Blood samples for PK will be collected at 15 min, 30 min, 45 min, 1h, 3h, 6h, and 12h postdose (Section 7.4).
- Vital signs (supine BP, HR, RR, and oral temperature) will be measured at 30 min, 45 min, 1h, 3h, and 12h postdose after 5 minutes in a supine position.
- Brief physical examination at 6h postdose.
- Blood and urine safety test at 6h postdose.
- Urine collection for PK during 0-12h hourly UC (each void collected separately) and 12-24h postdose, 6h intervals UC (cumulative collection 12-18h, and 18-24h postdose).
- Urine samples for renal injury biomarkers and creatinine (from the last void of the 0-12h collection) (Section 7.5.1).
- 12-lead ECG recording at 3h, 6h, and 12h postdose taken after 5 minutes in a supine position.
- Assessment of local reaction of injection site(s) 45 min, 6h, and 12h postdose (Section 7.3.7).
- Blood sampling for retention at 3h postdose.
- AEs assessment and change in concomitant medications.
- Meals will be served.

The study staff will encourage the subjects to drink at least one glass (approximately 250 mL) of fluids every hour up to 10h after dosing.

#### Day 2

- Vital signs (after 5 minutes in a supine position), BP, HR, RR, and oral temperature 24h).
- 12-lead ECG (24h) taken after 5 minutes in a supine position.

- Assessment of local injection(s) reaction (24h).

Blood sample collection:

- Safety lab tests (24h)
- PK (24h and 36h)
- Blood sampling for housekeeping proteins (24h).
- Urine collection :
  - Urinalysis (24h)
  - Urine PK, 12h intervals (cumulative 24h-36h and 36-48h collection)
  - Renal injury biomarkers and creatinine (24h and 36h urine void)
- AEs assessment and change in concomitant medications.

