## 7.2. Allowed Time Window Deviations

Allowed time window deviations are (assessments at screening, Day -1, and EOS not described here):

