### For laboratory samples

#### a. Blood samples

- Safety sampling: Day 1 and Day 29: 6h ( $\pm$  15 min), 24h ( $\pm$  15 min), 48h ( $\pm$  30 min). Other safety blood samples will be taken in the morning of Day 7, Day 14, Day 21, and Day 28.
- PK sampling: Day 1 and Day 29: predose, 15 min ( $\pm$  2 min), 30 min ( $\pm$  5 min), 45 min ( $\pm$  5 min), 1h ( $\pm$  5 min), 3h ( $\pm$  15 min), 6h ( $\pm$  15 min), 12h ( $\pm$  30 min),

24h ( $\pm$  1h), 36h ( $\pm$  1h), 48h ( $\pm$  1h), 72h ( $\pm$  1h). On other dosing days, the PK blood samples will be taken predose and 1h postdose ( $\pm$  5 min).

- Housekeeping proteins: Day 1 and Day 29: predose and 24h ( $\pm$  1h), 48h ( $\pm$  1h) postdose. On other dosing days the sample needs to be taken predose.
- Blood retention sampling: Day 1 and Day 29 predose and at 3h ( $\pm$  15 min) postdose. On other dosing days the sample needs to be taken predose.

b. Urine samples

- Safety sampling: Day 1 and Day 29: 6h ( $\pm$  30 min), 24h ( $\pm$  2h), 48h ( $\pm$  2h). Other safety urine samples will be taken in the morning of Day 7, Day 14, Day 21, and Day 28.
- PK sampling: Day 1 and Day 29: predose and during 0-12h ( $\pm$  15 min), 12-24h ( $\pm$  15 min), 24-48h ( $\pm$  15 min), and 48-72h ( $\pm$  15 min) postdose. And on Day 8, 11, 15, 18, 22, and 25 for creatinine.
- Renal injury biomarkers and creatinine sampling: predose and 12h sample from last void of the 0-12h collection ( $\pm$  30 min), 24h ( $\pm$  2h), 36h ( $\pm$  2h), 48h ( $\pm$  2h), and 72h ( $\pm$  2h) postdose. And on Day 8, 11, 15, 18, 22, and 25.

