3.2. General Methods

All data listings that contain an evaluation date will contain a relative study day (Rel Day). Pre-treatment and on-treatment study days are numbered relative to the day of the first dose of study drug which is designated as Day 1. The preceding day is Day -1, the day before that is Day -2, etc.

All output will be incorporated into Microsoft Word RTF or Adobe Acrobat PDF files, sorted and labeled according to the International Council on Harmonisation (ICH) recommendations, and formatted to the appropriate page size(s).

Tabulations will be produced for appropriate demographic, baseline, PK, and safety parameters. For categorical variables, summary tabulations of the number and percentage of subjects within each category (with a category for missing data) of the parameter will be presented. For continuous variables, the number of subjects, mean, median, standard deviation (SD), minimum, and maximum values will be presented.

Summary tabulations for general and safety analyses will be presented by treatment and dose (including placebo, all dose levels and all ELX-02) and separately by concentration (including Cohorts 3, 4, 5 and 6). Placebo will be pooled across cohorts and presented in one column. A total column for those receiving ELX-02, regardless of dose, will also be included. The placebo and the total columns will not be included in the summary tabulations for PK analyses.

Figures for PK concentrations will be presented by cohort and figures for PK parameters will be presented by dose. If differences in PK parameters (AUC, C_{max} , $t_{1/2}$) between final diluted injection concentrations are observed in the “by concentration” summary tables, figures for PK parameters will be presented by cohort. Details for figure presentation are described in [Section 4.3.3](#).

All data listings will be presented by cohort.

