3.4. Baseline Definitions

For all analyses, baseline will be defined as the most recent measurement prior to the first administration of study drug.

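### SAP 4.4.4 labels the laboratory baseline Day 1, but the only blood safety panel and urinalysis scheduled that day are 6 h postdose, which contradicts the predose baseline in SAP 3.4

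*SAP*

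**What the plan says.** SAP 4.4.4 (Laboratory Data) covers hematology, clinical chemistry, urinalysis and coagulation. It sets the change summaries as follows: "The actual value and change from baseline (Day 1) to each on-study evaluation will be summarized". The parenthesis has no predose qualifier. The shift-table sentence in the same section says only baseline and names no day.

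SAP 3.4 gives the general rule: "For all analyses, baseline will be defined as the most recent measurement prior to the first administration of study drug". It makes no exception for laboratory data.

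SAP 3.2 numbers study days "relative to the day of the first dose of study drug which is designated as Day 1", and calls the day before it Day -1. The two labels therefore mean different calendar days.

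Protocol 7.1 schedules safety laboratory tests at screening and on Day -1 ("Blood and urine safety tests (see Section 7.3.9 for more details"). On Day 1 it schedules them after dosing: "Blood and urine safety test at 6h postdose".

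**The concern.** Laboratory changes belong to the primary safety endpoint, which covers adverse events and other changes in safety parameters. Nephrotoxicity is an adverse event of interest, and Protocol 8.4.1 relies on creatinine measured before and after dosing. A change table is readable only if its reference value comes from before treatment.

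The laboratory section is the one place where the SAP attaches a day to baseline. The vital-sign, audiometry, ECG and renal-biomarker sections (4.4.5 to 4.4.8) leave the word unqualified. A programmer could fairly take the parenthesis as a deliberate specification for laboratory data. SAP 3.11 tabulates data by nominal visit, and selecting the Day 1 visit from the scheduled laboratory records returns the 6 h value.

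**Working it through.** The plan states no figure to reproduce. The check sets the SAP labels against the protocol's sampling schedule, then works out what the literal reading would do.

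**1. Is there a Day 1 predose safety panel?**

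- *Protocol 7.1, Day -1:* blood and urine safety tests are listed.
- *Protocol 7.1, Day 1 predose:* blood is for PK, housekeeping proteins and retention; urine is for PK, creatinine and renal injury biomarkers. There is no safety panel and no urinalysis. The retention blood is held in case a safety question arises and is not a planned laboratory assessment.
- *Protocol 7.1, Day 1 postdose:* blood and urine safety tests at 6 h.
- *Protocol 7.2, blood samples:* "Safety sampling: Day 1 and Day 29: 6h", followed by 24 h and 48 h. There is no predose entry, although the PK, housekeeping-protein and retention lines each list one.
- *Protocol 7.2, introduction:* "assessments at screening, Day -1, and EOS not described here". The absence of Day -1 from the window list therefore does not remove the Day -1 sample.

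For the four laboratory classes in SAP 4.4.4, the last scheduled predose sample is on Day -1 and the only Day 1 sample is at 6 h. Urine creatinine is different: it has a Day 1 predose sample.

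The wording elsewhere points the same way. Protocol 7.3.5 specifies Day 1 predose as the ECG baseline, and a predose ECG is scheduled that day. SAP 4.4.4 lacks that qualifier, and no matching laboratory sample exists.

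**2. What would the literal reading do?**

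For one subject and analyte, let L(-1) be the Day -1 value, L(6h) the Day 1 value and L(t) the value at a later evaluation t.

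- Under SAP 3.4: change at t = L(t) - L(-1).
- Under Day 1 read literally: change at t = L(t) - L(6h) = [L(t) - L(-1)] - [L(6h) - L(-1)].
- At t = 6 h the second formula gives L(6h) - L(6h) = 0 for every subject and analyte.
- At any later t, the first-6-hours change is subtracted from the result.

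The scheduled postdose evaluations are Day 1 at 6 h, Days 2, 3, 7, 14, 21 and 28, Day 29 at 6 h, Days 30 and 31, and end of study: 11 in all. Under the literal reading, 1 is zero by construction and the other 11 - 1 = 10 are shifted.

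**3. Would the placebo column put it right?**

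Only in part. In the ELX-02 minus placebo difference, the shift is the between-group difference in L(6h) - L(-1). Anything common to both arms cancels on average; an early drug effect does not.

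Protocol 1.2.2 gives a median time to peak of about 0.5 to 1.0 h. The 6 h sample therefore comes about 6 - 1.0 = 5.0 to 6 - 0.5 = 5.5 h after peak and is plainly a treated value.

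**4. Fasting.**

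Protocol 7.3.9 exempts the 6 h samples from the 8 h fast required of the other safety samples. Under the literal reading, fasted later samples would be compared with a reference that need not be fasted. Exempt does not mean fed, so this is a possible mismatch only.

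**The case against.** The strongest reply is that SAP 3.4 already settles the matter. It applies to all analyses, the Day -1 draw supplies its value, and a postdose baseline would require someone to breach it. The parenthesis may be loose shorthand for the start of dosing. A column of zero changes at 6 h would probably be noticed at the first table review. This stands in one respect: a reader might infer that the change tables will start from a treated value, and the documents do not support that. They show two conflicting instructions, one of which gives the right answer.

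Two other inferences also go too far.

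- *That the CTCAE shift tables start from Day 1.* The Day 1 label appears only in the change-summary sentence, so SAP 3.4 governs the shift tables directly.
- *That fluid intake makes the 6 h sample a diluted reference.* The predose water is an instruction, but the hourly postdose fluids are only encouraged. No document gives an effect of either on laboratory values, and placebo subjects follow the same regime.

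There are other safeguards. Actual values are summarized beside the changes, all laboratory data are listed by subject, grade 3 or higher values have their own listing, and clinically significant abnormalities are reported as adverse events. The creatinine-normalized biomarkers in SAP 4.4.8 carry no Day 1 label. Escalation depends on graded drug-related toxicity and high-frequency audiometry events, not on this table. An early effect would therefore not vanish from the report.

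None of this removes the conflict. The label in 4.4.4 is wrong against the schedule, and the SAP does not say which section prevails.

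**Conclusion.** The point holds as an inconsistency between SAP 4.4.4 and SAP 3.4 that leaves the baseline of the laboratory change summaries ambiguous. For hematology, chemistry, coagulation and urinalysis, the Day 1 label matches only a 6 h postdose sample. A post-treatment baseline could result; it is not a certainty.

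If it did result, the 6 h change would be zero by construction and any early laboratory effect would be absorbed into the baseline of the change tables. No numerical size can be given, because the documents contain no laboratory values.

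The conclusion assumes that Protocol 7.1 and 7.2 state the schedule completely. The Day -1 and Day 1 rows of Table 1 were not legible in the text available and should be checked against it. It does not extend to urine creatinine or to the shift tables as they are worded.

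**What to change.** In SAP 4.4.4, replace the words baseline (Day 1) with: *baseline (last value before first dose per Section 3.4, normally Day -1)*. Add one sentence stating that the same baseline applies to the CTCAE shift tables, so that the section cannot be programmed with two references.

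The cost is one phrase and one sentence in the SAP. It needs no new data, no protocol amendment and no change to study conduct. If laboratory programs already exist, confirm that they select the last predose record and not the Day 1 nominal visit.

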**Table 2: Safety Test**

Safety Blood Tests			
Hematology and Coagulation			
Red Blood Cell (RBC) count	Mean corpuscular hemoglobin (MCH)	White blood cells (WBC)	International normalized ratio (INR)
Hemoglobin	Mean corpuscular hemoglobin concentration (MCHC)	Platelets	WBC differential count
Hematocrit	Mean cell volume (MCV)	Prothrombin	
Biochemistry			
Total Protein	Aspartate aminotransferase (AST)	Alkaline Phosphatase (ALP)	Blood urea nitrogen
Albumin	Gamma glutamyl transferase (GGT)	Glucose	Serum Creatinine
Total Bilirubin	Lactate dehydrogenase (LDH)	Natrium (Sodium)	Glomerular filtration rate (GFR), (MDRD) (only at screening visit)
Alanine aminotransferase (ALT)	Creatine Phosphokinase	Potassium	
Hormones			
Serum $\beta$ -human chorionic gonadotropin (HCG) (screening only)	FSH (screening only)		
Serology (screening and follow-up only)			
HIV Ab	HBsAg	HCV Ab	
Urine Tests			
Urinalysis			
Proteins	Ketones	pH	Specific Gravity (SG)
Glucose	Urobilinogen	RBC	Bilirubin
Urine protein and Albumin (screening and EOS)			

Urine Biochemistry						
Creatinine						
Hormones						
Urine pregnancy test (all women, regardless of childbearing potential) Day -1, Day 7, Day 14, Day 21, Day 28, Day 36						
Drugs of Abuse (screening) Day -1, Day 7, Day 14, Day 21, and Day 28.						
Cannabinoids (THC)	Amphetamines	Benzodiazepines	Opiates			
Serum alcohol						

Abnormal safety tests may be confirmed by a single repeat, if deemed necessary.

The following microscopic parameters will be tested: RBC, WBC, bacteria, epithelial cells, granular casts, and hyaline casts.

After dosing, all lab tests outside the normal range will be repeated as clinically indicated until the values return to normal, or until the etiology has been determined and the condition considered stable. Abnormal laboratory test results that are considered to be clinically significant by the Investigator will be reported as an AE.

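### By-visit laboratory summaries take the last of any same-time repeats, and only abnormal values are repeated, so a one-directional drug shift would be understated

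*SAP*

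**What the plan says.** **What is tabulated.** SAP 4.4.4: "The actual value and change from baseline (Day 1) to each on-study evaluation will be summarized for each clinical laboratory parameter". For duplicates: "In the event of repeat values, the last non-missing value per study day/time will be used". The next sentence limits the tables: "Laboratory results recorded at unscheduled visits will not be tabulated".

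**When a test is repeated.** The notes to Table 2 in Protocol 7.3.9 give two triggers, and both depend on the result. The first is discretionary: "Abnormal safety tests may be confirmed by a single repeat, if deemed necessary". The second applies after treatment starts: "After dosing, all lab tests outside the normal range will be repeated as clinically indicated until the values return to normal". That sentence also allows repeats to stop once the cause is known and the subject is stable. No rule calls for repeating an in-range value.

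**What else the SAP shows.** SAP 4.4.4 has shift tables of CTCAE grade "from baseline to worst value and from baseline to last value on study will be presented", and adds: "Both scheduled and unscheduled visits will be included in shift tables". All laboratory data are listed, with a separate listing of grade 3 and above. SAP 3.4 takes baseline as the latest measurement before the first dose.

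**The concern.** The choice between a first and a repeat value is harmless if repeats occur regardless of the result. Here the result decides whether there is a repeat. An in-range value stays as drawn, while an out-of-range value may be exchanged for a second draw that tends, by regression to the mean, to lie closer to normal.

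Changes in safety parameters at ascending doses are part of the first primary endpoint (Protocol 2.2.1). Nephrotoxicity is an adverse event of interest (Protocol 8.4), and creatinine is followed to detect renal injury (Protocol 8.4.1). A cohort has only 6 subjects on ELX-02, so one replaced value can visibly change its mean. The tables at stake are the by-visit means and mean changes for laboratory parameters.

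**Working it through.** **No figure to reproduce.** The plan gives no laboratory variance, repeat rate or repeat correlation, and no formal sample size. The sizes below therefore rest on assumptions; only the direction follows from the documents.

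**Can the rule operate?** Yes. Apart from the Day 36 visit, the post-dose safety bloods fall during or at the start of confinement: 6, 24 and 48 hours after the Day 1 and Day 29 doses, and Days 7, 14, 21 and 28 (Protocol 7.1). A same-day repeat then needs no unscheduled visit. SAP 3.11 tabulates by the nominal visit in the eCRF, so a repeat filed there under the same day/time displaces the first result.

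**Model (assumed).** The first value X1 is Normal with mean δ (the drug shift) and SD 1, and the normal range is ±1.96 SD. Every out-of-range value is repeated once, the repeat X2 has correlation ρ with X1, and X2 replaces X1.

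**Formula.** Given X1, the expected value of X2 − X1 is −(1 − ρ)(X1 − δ). Averaging over out-of-range X1 gives

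bias = −(1 − ρ) × [φ(1.96 − δ) − φ(−1.96 − δ)], where φ is the standard normal density.

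For δ = 1.0: φ(0.96) − φ(−2.96) = 0.2516 − 0.0050 = 0.2466. Multiplying by (1 − ρ) gives 0.123, 0.074 and 0.025 for ρ = 0.5, 0.7 and 0.9.

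| True shift (SD) | Reported, ρ = 0.5 | ρ = 0.7 | ρ = 0.9 |
|---|---|---|---|
| 0 | 0.00 | 0.00 | 0.00 |
| 0.5 | 0.44 | 0.46 | 0.49 |
| 1.0 | 0.88 | 0.93 | 0.98 |
| 1.5 | 1.32 | 1.39 | 1.46 |
| 2.0 | 1.80 | 1.88 | 1.96 |

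Simulation with 1,000,000 draws per case agreed with the formula to about 0.001 SD. Applying the same replacement to an unshifted baseline left the mean change the same to within 0.002 SD.

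**Spread and out-of-range share (simulation).**
- No shift: the SD falls from 1.00 to 0.91–0.98, and the out-of-range share from 5.0% to 0.9%–3.0%.
- Shift of 1.0 SD: the out-of-range share falls from 17.0% to 6.8%–12.5%.

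**Sensitivity to the assumptions.**
- Up to three repeats until normal, all under one day/time: a 1.0 SD shift is reported as 0.83–0.96 SD.
- Only half of the out-of-range values repeated, chosen without regard to size: the loss halves. For δ = 1.0 and ρ = 0.5 it is 0.5 × 0.123 = 0.06 SD.

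**One subject in a cohort of 6.** A transient +3 SD value adds 3/6 = 0.50 SD to the cohort mean if the first value is used. If the repeat is back at the mean and the last value is used, it adds 0. The chance of at least one abnormal value among 6 subjects is 1 − 0.95^6 = 26% at 5% per subject and 1 − 0.90^6 = 47% at 10%.

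**The case against.** **The reach is narrow.** Results at unscheduled visits stay out of the by-visit tables, and following an abnormality until it resolves will often need another day or visit. A repeat recorded there leaves the scheduled abnormal value in place. This stands, and it confines the point to repeats under the same study day/time. A reader might infer from the until-normal wording that long chains of repeats routinely feed the tables. The documents do not support that: the wording is qualified by clinical indication, and repeats may also end once the abnormality is explained and stable.

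**The size may be small.** Repeats are discretionary, subjects are healthy volunteers screened for clinically relevant laboratory abnormalities, and same-day repeats may agree closely. Low values are repeated too, so without a shift the two directions cancel in the mean. All of this stands. It bears on size and leaves the direction under a one-sided shift unchanged.

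**Signals have other routes.** Shift tables, listings, adverse event reporting of clinically significant results, an acute renal failure query (SAP 4.4.3) and the KIM-1 and clusterin summaries (SAP 4.4.8) remain. The escalation rules in Protocol 3.2 rest on graded toxicity and high-frequency audiometry events, with no rule based on laboratory means. This also stands, but none of it corrects the by-visit means.

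**First value has its own cost.** In a cohort of 6, a transient outlier kept in the table moves the mean by 0.50 SD in the example above, more than the average one-repeat bias. That is a real trade-off. The median, already planned in SAP 3.2, softens it.

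**Conclusion.** The point holds for by-visit laboratory means and changes from baseline. The rule replaces values selectively, and a drug shift in one direction would be understated. Under the stated assumptions a true 1.0 SD shift is reported as about 0.88 to 0.98 SD. The true size cannot be derived from the documents and may be smaller.

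Two stronger readings are not supported:

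- **That the bias is always larger in the group with more abnormal values.** In a simple model with an upper limit only and independent error of SD s, the bias is −s × φ(z), where z is the distance from the true mean to the limit in units of s. For abnormal rates of 15.9%, 50.0% and 84.1% it is −0.24s, −0.40s and −0.24s, so it peaks at 50% and then falls. For a true mean 2s below the limit it is only −0.05s.
- **That the last-value rule empties the shift tables of their worst values.** The shift tables have their own paragraph, which names the worst value and includes unscheduled visits. The SAP does not say whether a superseded same-time result counts, so this needs only a clarification.

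Overall this is a cheap improvement to a descriptive analysis, and abnormal results are not lost from the report.

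**What to change.** In SAP 4.4.4, replace the sentence on repeat values with:

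> By-visit summaries use the first valid scheduled value for each study day/time; a repeat replaces it only if the first sample is documented as invalid. Worst value in the shift tables is taken over all results, including repeats.

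For consistency, apply the same rule to repeats at the laboratory baseline time point, with a matching laboratory exception in SAP 3.4, which otherwise takes the latest predose value.

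**Cost.** Short edits in two SAP sections and one derivation flag, with no new data. The downside is that a valid but transient outlier stays in the mean of a small cohort; the median shown beside it helps the reader judge its influence.
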